6.4.1.2.1 Chemotherapy Hematologic Toxicities

Febrile Neutropenia

Febrile neutropenia is defined as follows:

• Grade 2 fever (temperature $\geq 38.1^{\circ}$ C) concomitant with Grade 4 neutropenia (ANC < $500/\text{mm}^3$) requiring intravenous antibiotics and/or hospitalization.

Fever should be graded using the CTCAE version 4.03 grading system. The reported temperature should be the axillary temperature.

In cases of febrile neutropenia, the following approach is recommended:

- Hospital admission except where outpatient care may be suitable.
- Pre-antibiotic evaluation (e.g., antibiogram).
- White blood cell count with differential and blood culture should be performed.
- Dose reductions and commencement of an antibiotic treatment as outlined in Table 6.6.

In case of febrile neutropenia, blood counts must be done every 2 days until recovery to ANC ≥500/mm³ or temperature < 38.1°C.

Table 6.6 Chemotherapy Dose Reduction and Treatment for Febrile Neutropenia

Adverse Event	Treatment
Febrile neutropenia Documented infection	1) The first episode of febrile neutropenia or documented infection will result in antibiotic treatment and reduction by 20% of both the cisplatin and 5-FU doses while maintaining the duration of 5-FU infusion of 5 days (or dose reduction of carboplatin to AUC 4 if applicable)
	2) If there is a second episode despite dose reduction, the subject must receive prophylactic antibiotics (quinolone) during the subsequent cycles and a second dose reduction by 20% of both cisplatin and 5-FU during the subsequent cycles3) If there is a third episode, the subject will be withdrawn

Criteria for Dose Reductions Based on Hematologic Results

If a subject's blood sample on the scheduled day of treatment shows abnormal hematology results, chemotherapy dose may need to be reduced. If any of the hematologic criteria presented in Table 6.7 are met, a dose reduction of chemotherapy is required.

Table 6.7 Criteria for Dose Reductions Based on Hematologic Results on the Schedule Day of Treatment

Neutropenia	Grade 3 (500-999/mm³)	Chemotherapy treatment delay until ≤ Grade 1 (≥ 1500/mm³)
	Grade 4	Chemotherapy treatment delay until no more than Grade 1; dose reduction of all further doses of cisplatin or carboplatin and 5-FU by 20%
Thrombopenia	Grade 1	Chemotherapy treatment delay until thrombocytes > 100000/mm ³
	At least Grade 2	Chemotherapy treatment delay until thrombocytes > 100000/mm³; dose reduction of all further doses of cisplatin or carboplatin and 5-FU by 20%

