6.4.1.2 Dose Reductions of Chemotherapy

Every effort will be made to administer the full doses of cisplatin/carboplatin and 5-FU.

Dose reductions are always based on the dose of the previous cycle. Only 2 dose reductions for cisplatin and 5-FU and 1 dose reduction for carboplatin are permitted. If further toxicity occurs or the criteria for resuming treatment are not met, the subject must be withdrawn from chemotherapy (see Table 6.5).

Table 6.5 Dose Reductions for Chemotherapy

	Dose reduction levels	Dosage ¹
Cisplatin	0	75mg/m ²
	-1 (decreased by 20%)	60mg/m ²
	-2 (decreased by 20% from -1 level)	48mg/m ²
Carboplatin ² -	0	AUC 5
	-1 (decreased by 20%)	AUC 4
5-Fluorouracil	0	750mg/m ²
	-1 (decreased by 20%)	600mg/m ²
	-2 (decreased by 20% from -1 level)	480mg/m ²

Abbreviation: AUC, area under serum concentration time curve.

- 1 The doses which have been reduced for toxicity must not be re-escalated.
- 2 Carboplatin can be considered, if the subject experiences a nonhematologic toxicity. The starting dose of carboplatin would be the first dose level of AUC 5 at the Investigator's discretion.

Dose adjustments are to be made according to the body system showing the greatest degree of toxicity experienced during the previous cycle. Toxicities will be graded using the CTCAE version 4.03.

All implemented dose reductions are permanent. The doses must be modified according to the lowest hematology values and the highest degree of nonhematologic toxicities observed at the scheduled date of chemotherapy. If a subject develops several different toxic effects and there are conflicting recommendations, the dose modification will be based on the AE on the scheduled day of treatment.

Dose reduction and delays and related management will be documented in the subject's medical record and in the related section in the eCRF.

If a subject has a Grade 3 or 4 toxicity after 2 dose reductions, or if a treatment delay is longer than 3 consecutive weeks, then the discontinuation of chemotherapy treatment has to be considered.

For those in Arm A, chemotherapy will not be delayed for cetuximab-related toxicities.

Major toxicities observed with cisplatin: nephrotoxicity; ototoxicity; myelodepression with leukopenia, thrombocytopenia and anemia; infectious complications; nausea and vomiting; and peripheral neuropathies.

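### The sentence above Table 6.7 requires a chemotherapy dose reduction for every criterion, but two of the four rows order a delay only

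*Protocol*

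**What the plan says.** In Protocol Section 6.4.1.2.1, the paragraph on blood counts found on the scheduled treatment day has two sentences. The first says that the "chemotherapy dose may need to be reduced". The second goes further: "If any of the hematologic criteria presented in Table 6.7 are met, a dose reduction of chemotherapy is required". It names no drug and no size of reduction.

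Table 6.7 then gives four rows:

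- Neutropenia Grade 3: "Chemotherapy treatment delay until ≤ Grade 1 (≥ 1500/mm³").
- Neutropenia Grade 4: "Chemotherapy treatment delay until no more than Grade 1; dose reduction of all further doses of cisplatin or carboplatin and 5-FU by 20" per cent.
- Thrombopenia Grade 1: "Chemotherapy treatment delay until thrombocytes > 100000/mm"³.
- Thrombopenia Grade 2 or worse: the same platelet delay, plus "dose reduction of all further doses of cisplatin or carboplatin and 5-FU by 20" per cent.

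Section 6.4.1.2 sets the consequences of a reduction: "All implemented dose reductions are permanent". It allows two reductions each for cisplatin and 5-FU and one for carboplatin. If toxicity recurs after that, the subject comes off chemotherapy.

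**The concern.** A site with a Grade 3 neutrophil count or a Grade 1 platelet count on the treatment day has two instructions. The sentence makes a reduction mandatory; the row asks only for recovery.

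The choice cannot be undone for that patient. A reduction made under the sentence is permanent and uses up a limited allowance, which brings forced withdrawal from chemotherapy one step nearer.

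It can also reach the reported exposure data. The number of dose reductions is a safety variable in Protocol Section 8.3.3. SAP Section 15.1 classifies each subject by minimum relative dose, and SAP Section 17.1.2 tabulates adverse events leading to chemotherapy dose reduction. If sites differed in which text they followed, part of what those tables show would be site interpretation and not toxicity.

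**Working it through.** The plan states no figure to reproduce here. The check is a comparison of texts, followed by the dose arithmetic for one event.

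**Step 1. Sentence against rows.**

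| Table 6.7 row | Sentence requires a reduction | Row orders a reduction | Agree |
|---|---|---|---|
| Neutropenia Grade 3 | Yes | No, delay only | No |
| Neutropenia Grade 4 | Yes | Yes, 20% | Yes |
| Thrombopenia Grade 1 | Yes | No, delay only | No |
| Thrombopenia Grade 2 or worse | Yes | Yes, 20% | Yes |

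The sentence is wrong for 2 of 4 rows.

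**Step 2. Does another rule settle it?** The only conflict rule, in Section 6.4.1.2, begins "If a subject develops several different toxic effects and there are conflicting recommendations". It deals with different toxicities that point different ways, not with one toxicity under two instructions. Neither document ranks the text above the table or the reverse.

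**Step 3. Which text is intended?** The evidence favours the rows:

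- The first sentence of the paragraph treats a reduction as possible, not certain.
- Both toxicities in Table 6.7 pair a lower-grade delay with a higher-grade delay plus reduction. If every row implied a reduction, that distinction would have no purpose.
- Four toxicities in Table 6.8 (mucositis, diarrhea, hand-foot syndrome, other organ toxicity) use the same pairing. Section 6.4.1.2.2, which introduces that table, has no sentence making a reduction compulsory.
- Section 6.4.1.1.4 requires only a delay when neutrophils are below 1.5 × 10⁹/L or platelets below 100 × 10⁹/L. These are the recovery levels used in the two delay-only rows (1500/mm³ and 100000/mm³).
- Section 6.4.1.2 states an aim of giving full doses.

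**Step 4. Size for one event from full dose.** The sentence gives no percentage, so the 20% step of Table 6.5 is assumed.

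| Drug | Following the row | Following the sentence |
|---|---|---|
| Cisplatin | 75 mg/m² | 75 × 0.8 = 60 mg/m² |
| 5-FU | 750 mg/m²/day | 750 × 0.8 = 600 mg/m²/day |
| Carboplatin | AUC 5 | 5 × 0.8 = AUC 4 |

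**Step 5. Effect on the SAP exposure table.** In SAP Section 15.1 the category from 70% to below 90% is 52.5 to <67.5 mg/m² for cisplatin and 525 to <675 mg/m²/day for 5-FU. Since 60/75 = 80% and 600/750 = 80%, a subject otherwise at full dose drops from the category of at least 90% to this one for both drugs.

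**Step 6. How many cycles an amendment could still reach.** SAP Section 5 dates the last protocol version 26 February 2018. Protocol Section 5.1 anticipates recruitment to the fourth quarter of 2017. For a subject randomized on 31 December 2017 (an assumption) with no delays, cycles start every 21 days: Cycle 2 on 21 January, Cycle 3 on 11 February, Cycle 4 on 4 March, Cycle 5 on 25 March and Cycle 6 on 15 April 2018. Only Cycles 4 to 6 start after the protocol date.

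**The case against.** The strongest reply is that the sentence cannot be carried out alone. It gives no drug and no amount, so a site has to read the row, and each row is a complete instruction for its grade. To cut the dose for Grade 1 thrombopenia, a site would have to disregard the row, the restart rule in Section 6.4.1.1.4 and the full-dose aim in Section 6.4.1.2. The subsection and table are titled as criteria for dose reductions, so the sentence could be read as covering only the rows that contain one, though that reading is strained.

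The statistical reach is also small. The chemotherapy rules are the same in both arms, and Protocol Section 8.5.4 plans no formal safety comparisons. An unneeded reduction is not on the important-deviation list in SAP Appendix 1, so it moves nobody out of the per-protocol set. A correction would also come late and might need approval before use (Protocol Section 10.5).

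Most of this stands. Many clinicians would probably follow the row, and what remains on the analysis side is a possible shift between descriptive categories. These arguments limit the weight of the point. They do not make the sentence true for the two delay-only rows, and in a dosing section an instruction that is mandatory as worded should not depend on readers setting it aside.

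**Conclusion.** The inconsistency is real and the sentence is wrong as written for two of the four rows. The rows are almost certainly what was meant. Severity is minor. For a single patient at a site that follows the sentence, the cost is one unneeded permanent 20% step and one used reduction, assuming the Table 6.5 step and its application to both the platinum drug and 5-FU. The documents do not say how often these counts would occur or which text sites followed. No trial-level effect is therefore claimed: no arm imbalance, and no change to the hazard ratio, sample size or error rates.

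**What to change.** Replace the second sentence with wording such as: *When a blood count meets a criterion in Table 6.7, the action in the matching row applies: delay alone, or delay with a 20% dose reduction.* Widen the subsection heading and table title to cover delays as well as reductions, and notify sites. If the sponsor did intend a reduction for Grade 3 neutropenia or Grade 1 thrombopenia, write it into those two rows instead.

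The cost is a short text change in an amendment and a site memo, with no added patients, visits or procedures. If recruitment ran to plan, few cycles would be left to benefit.

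If chemotherapy is already complete at all sites, state in the clinical trial report which text sites applied when giving the number of dose reductions. That takes more work than the amendment, because counts on treatment days would have to be compared with doses given, site by site.

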6.4.1.2.2 Nonhematologic Toxicities

If a subject has a Grade 3 or 4 toxicity, as defined in Table 6.8, after 2 dose reductions, or if a treatment delay is longer than 3 consecutive weeks, then the discontinuation of chemotherapy treatment has to be considered.

Table 6.8 Criteria for Dose Reductions Based on Nonhematologic Toxicities on the Scheduled Day of Treatment

Toxicity	Grade ¹	Action to be taken
Mucositis	Grade 1	Delay chemotherapy treatment until Grade 0
	> Grade 1	Delay chemotherapy treatment until Grade 0; dose reduction of all further doses of 5-FU only by 20%
Diarrhea	Grade 1	Delay chemotherapy treatment until Grade 0
	> Grade 1	Delay chemotherapy treatment until Grade 0; dose reduction of all further doses of 5-FU only by 20%
Hypercreatinemia	≥ Grade 1	Delay chemotherapy treatment until Grade 0, change cisplatin to carboplatin
Ototoxicity	Grade 2	Dose reduction of all further doses of cisplatin by 20%
	> Grade 2	Delay chemotherapy treatment until ≤ Grade 2, change cisplatin to carboplatin
	> Grade 3	Stop carboplatin
Hand-foot syndrome	Grade 2	Delay chemotherapy treatment until ≤ Grade 1
	> Grade 2	Delay chemotherapy treatment until ≤ Grade 1; dose reduction of all further doses of 5-FU by 20%
Other organ toxicity ²	Grade 2	Delay chemotherapy treatment until Grade 1
	> Grade 2	Delay chemotherapy treatment until Grade 1 ³ ; dose reduction of all further doses of platinum-based treatment and 5-FU by 20% (or dose reduction of carboplatin to AUC 4 if applicable)
Sensory neuropathy	Grade 2	Dose reduction for all further doses of cisplatin by 20%
	> Grade 2	Stop cisplatin, change cisplatin to carboplatin
	> Grade 3	Stop carboplatin

5-FU: 5-fluorouracil.

The results of hematology and blood biochemistry analyses must be available before the start of each cycle of chemotherapy.

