5.3.2 Exclusion Criteria

Subjects are not eligible for this trial if they fulfill any of the following criteria:

- 1. Prior systemic chemotherapy, except if given as part of multimodal treatment for locally advanced SCCHN that was completed more than 6 months before randomization.
- 2. Major surgery or irradiation within 4 weeks before randomization.
- 3. Previous treatment with monoclonal antibody or signal transduction inhibitors targeting EGFR.
- 4. Nasopharyngeal carcinoma.
- 5. Known allergic reaction against any of the components of the trial treatment.
- 6. Active infection including active tuberculosis, known and declared human immunodeficiency virus (HIV) infection, or active hepatitis B/C virus (HBV/HCV) infection resulting in an impaired liver function or cirrhosis (see Section 7.2.4).
- 7. History of organ allograft, autologous/allogeneic stem cell transplantation, and renal replacement therapy.
- 8. Asymptomatic severe hypertension or hypertensive crisis defined as systolic blood pressure ≥180 mmHg and/or diastolic blood pressure ≥110 mmHg under resting conditions.
- 9. Impaired cardiac function, evidenced by any of the following conditions:
 - o Left ventricular ejection fraction < 45%
 - Serious arrhythmia
 - Unstable angina pectoris
 - o Congestive heart failure New York Heart Association class III or IV
 - o Myocardial infarction within the 12 months before randomization
 - o Pericardial effusion.
- 10. Known central nervous system metastasis and/or leptomeningeal disease. Subjects with neurological symptoms should undergo a CT/MRI of the brain to exclude brain metastasis.
- 11. Known uncontrolled diabetes mellitus, pulmonary fibrosis, interstitial lung diseases, acute pulmonary diseases, or liver failure.
- 12. Peripheral neuropathy or hearing loss ≥Grade 2.
- 13. Subjects not recovered from any acute effects of prior surgery, chemotherapy, or radiation therapy, that is, to \leq Grade 1 (CTCAE, version 4.03). Chronic late toxicities resulting from

prior radiation and/or surgery (pharyngeal/laryngeal toxicity, i.e., xerostomia, speech, swallowing abnormalities etc.) are permitted if nutritional status is stable.

- 14. Known alcohol and/or drug abuse.
- 15. Medical or psychological condition that would not permit the subject to complete the trial or sign informed consent.

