6.4.1.1.4 Criteria for Starting the Next Cycle of Chemotherapy

Before starting the next cycle of chemotherapy, the following criteria must be fulfilled:

- Absolute neutrophil count (ANC) is $\ge 1.5 \times 10^9 / L$.
- Platelet count is $\geq 100 \times 10^9 / L$.
- Nonhematologic chemotherapy-related toxicities have resolved to ≤ Grade 1 or baseline (excluding weight loss, skin reactions, paronychia, fatigue, ototoxicity or neurotoxicity which must have resolved to ≤ Grade 2).

If these criteria are not met, the start of the next cycle must be delayed to allow for recovery. If a delay of more than 21 days is necessary as a result of an unresolved toxicity, one or both of the chemotherapeutic drugs should be discontinued.

If the start of the next cycle must be delayed due to either a cisplatin/carboplatin-, or 5-FU-related toxicity, the start of the other compound should also be postponed. However, if either cisplatin/carboplatin or 5-FU dosing must be permanently discontinued, dosing should be continued with the remaining compound according to the schedule.

The BSA must be recalculated and the cisplatin and 5-FU doses adapted accordingly before each subsequent cycle (for formula see Section 6.4.1.1.1). A delay in the next cycle of up to 3 calendar days from the calculated Day 1 of that cycle for administrative reasons such as a weekend is at the discretion of the treating Investigator.

For those in Arm A, in case of cetuximab-related toxicity, chemotherapy will not be delayed and the planned schedule for administration should be maintained. If cetuximab treatment is terminated for a cetuximab-related toxicity, chemotherapy will be continued. If chemotherapy is completely terminated for a related toxicity, cetuximab may be continued as monotherapy until either PD, as assessed by the Investigator, an unacceptable toxicity or withdrawal of consent.

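### Protocol Section 6.4.1.1.4 and Table 6.8 set different recovery thresholds for mucositis, diarrhea and creatinine before the next chemotherapy cycle, and nothing says which governs

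*Protocol*

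**What the plan says.** Protocol Section 6.4.1.1.4 gives the conditions for the next cycle: "Before starting the next cycle of chemotherapy, the following criteria must be fulfilled". The nonhematologic condition is "Nonhematologic chemotherapy-related toxicities have resolved to ≤ Grade 1 or baseline". The exceptions are "excluding weight loss, skin reactions, paronychia, fatigue, ototoxicity or neurotoxicity which must have resolved to ≤ Grade 2". Mucositis, diarrhea and creatinine are not among them, so the general threshold applies to all three. The section then ties delay to its own list: "If these criteria are not met, the start of the next cycle must be delayed to allow for recovery".

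Table 6.8 in Section 6.4.1.2.2 gives actions by toxicity on the scheduled day of treatment:

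- Mucositis and diarrhea at Grade 1: "Delay chemotherapy treatment until Grade 0".
- Mucositis and diarrhea above Grade 1: the same endpoint with a 5-FU reduction, "Delay chemotherapy treatment until Grade 0; dose reduction of all further doses of 5-FU only by 20"%.
- Hypercreatinemia at Grade 1 or above: "Delay chemotherapy treatment until Grade 0, change cisplatin to carboplatin".

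The general threshold from Section 6.4.1.1.4 is printed again with the Table 6.8 footnotes. The only marker 3 in the table is on the other-organ-toxicity row, at the entry above Grade 2.

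**The concern.** Two parts of the protocol answer the same question: how far must mucositis, diarrhea or raised creatinine recover before chemotherapy resumes? One accepts Grade 1 or the baseline grade. The other names Grade 0 and does not mention baseline. A site reading the section headed as the criteria for the next cycle can treat a subject whom a site reading Table 6.8 would hold.

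Chemotherapy is given in both arms, and holding it has consequences in the plan. Long delays lead towards stopping drugs, some are recorded as important protocol deviations, and all longer delays enter the exposure tables. If sites apply different thresholds, those outputs partly describe how the protocol was read rather than how the treatment was tolerated. Safety is also involved, because the threshold decides whether a subject is dosed with a toxicity still present.

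**Working it through.** **1. The two rules compared on the scheduled day, for mucositis, diarrhea and creatinine**

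| Situation | Section 6.4.1.1.4 | Table 6.8 | Same decision? |
|---|---|---|---|
| Grade 0 | condition met | no delay | yes |
| Grade 1 | condition met | delay until Grade 0 | no |
| Grade 2 or higher, above baseline | delay | delay | yes, while it lasts |
| Recovered from Grade 2 or higher to Grade 1 | condition met | delay continues until Grade 0 | no |
| At a nonzero baseline grade | condition met through the baseline clause | no baseline clause | no |

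The rules part in three situations and agree in the others.

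**2. Can those situations arise?** The first two need only ordinary toxicity. For creatinine, SAP Appendix 3 places Grade 1 at more than 1 and up to 1.5 times baseline, or above the upper limit of normal and up to 1.5 times that limit. Read literally, any rise over baseline is Grade 1. A nonzero baseline is possible because exclusion criterion 13 ("Subjects not recovered from any acute effects of prior surgery, chemotherapy, or radiation therapy") uses Grade 1 as its recovery level, so residual Grade 1 effects do not exclude a subject.

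**3. Search for a precedence rule.** Section 6.4.1.2 has a sentence on conflicting recommendations, but it concerns several different toxic effects in one subject, not two thresholds for one toxicity. The repeated footnote is marked only on the other-organ-toxicity row. Neither section refers to the other on this threshold. None was found.

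**4. What a delay leads to**

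- Section 5.1: chemotherapy may be delayed by at most 21 + 3 = 24 days, then must stop.
- Section 6.4.1.1.4: after more than 21 days, one or both drugs should be discontinued.
- Sections 6.4.1.2 and 6.4.1.2.2: after more than 3 consecutive weeks (3 × 7 = 21 days), discontinuation has to be considered.
- SAP Appendix 1: continuing chemotherapy after more than 21 days of delay due to toxicity is an important deviation. It is not classed as clinically important, so it does not remove a subject from the per-protocol set.

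**5. Illustration with the SAP's cisplatin formulas (Section 15.2).** Assume six full doses of 75 mg/m² (6 × 75 = 450) and one hold for Grade 1 diarrhea, lasting 7 days or, at the other end, 21 days. These durations are assumptions.

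- Site that doses on time: duration (5 × 21 + 21) / 7 = 18 weeks; dose intensity 450 / (18/3) = 75; relative dose intensity 100%; no delay.
- Site that holds 7 days: interval 28, counted delay 28 − 24 = 4 days (3-8 day category); duration (105 + 7 + 21) / 7 = 19 weeks; 450 / (19/3) = 71.05; 71.05 / 75 = 94.7%.
- Site that holds 21 days: interval 42, counted delay 42 − 24 = 18 days (16 days or more); duration (105 + 21 + 21) / 7 = 21 weeks; 450 / (21/3) = 64.29; 64.29 / 75 = 85.7%.

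So the same clinical finding can be reported as no delay or as a delay in the longest category. Relative dose intensity for the same six doses ranges from 100% to 85.7%.

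**The case against.** The strongest reply is that the two texts can be read together. Section 6.4.1.1.4 states conditions that must be met; it does not say that meeting them is enough. Table 6.8 could then be a stricter layer for named toxicities. Its rows support this, since they set different endpoints on purpose: Grade 0 here, Grade 1 for hand-foot syndrome, Grade 2 for ototoxicity. The footnote marker suggests that the general threshold was meant for the residual row.

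This stands in part. A reader might infer that the same subject is both permitted and forbidden to start the next cycle. The documents do not support that, because a site that waits for Grade 0 complies with both texts. But the layered reading is nowhere stated. It would leave the baseline clause without effect for these three toxicities, and Section 6.4.1.1.4 requires delay only when its own criteria are not met. The alternative reading therefore remains reasonable.

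A reader might also infer that a subject who enters with Grade 1 mucositis can never satisfy Table 6.8 and must stop chemotherapy. That goes too far. It applies only while the grade persists, and the stopping language ranges from must stop to consider stopping. Section 6.4.1.2 bases dose adjustments on toxicity in the previous cycle, and Section 7.4.1.1 does not count unchanged baseline conditions as adverse events, so it is unclear that such a finding triggers the table. Subjects with recurrent disease only must also have finished radiotherapy more than 6 months before screening imaging. What remains is that the handling of a nonzero baseline is unstated.

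**Conclusion.** The inconsistency is real. Two thresholds are given for the same decision, for three named toxicities, without an order of precedence. It is an ambiguity that sites can resolve differently, not a strict contradiction. Clarification is worthwhile because it bears on uniform dosing, patient safety, the delay and exposure summaries, and the count of important deviations.

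Its size in subjects cannot be given. A reader might apply an assumed rate, for example 20-40% of 240 subjects, or 48-96 (0.20 × 240 and 0.40 × 240), but no document supports any such rate. The figures in the illustration show only how one hold would be reported, under the assumed durations.

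A reader might also infer that the choice of threshold biases PFS or affects the arms differently, since Table 3.1 lists mucositis and diarrhea among the effects of cetuximab. The documents do not establish this. Sections 6.4.1.1.4 and 6.4.1.2 say that chemotherapy in Arm A is not delayed for cetuximab-related toxicity. Table 6.8 does not repeat that rule in its mucositis and diarrhea rows, so how attribution works there is a further open point. The primary analysis, a stratified Cox model in all randomized subjects, does not use either threshold. Any effect on PFS would be indirect and is not quantified.

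**What to change.** Reconcile Section 6.4.1.1.4, the mucositis, diarrhea and hypercreatinemia rows of Table 6.8, and the footnote that repeats the general threshold. The revised text should:

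- state which threshold governs for these three toxicities, with a cross-reference in each place;
- state how a nonzero baseline grade is handled;
- state how mucositis or diarrhea attributed to cetuximab is handled, given that chemotherapy is not to be delayed for cetuximab-related toxicity.

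Which threshold applies is for the clinical team to decide; none is proposed here. The cost is a protocol clarification and a communication to sites. The sample size, primary endpoint and primary analysis need no change.
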